1.5 Data Sharing

As a member of the International Stroke Genetic Consortium, Wake Forest collaborates to identify medical, environmental and genetic risk factors and causes of stroke to better care for our patients.

The Ethnic/Racial Variations of Intracerebral Hemorrhage (ERICH) study originally recruited over 3000 cases of spontaneous hemorrhage with equal power among white, black and Hispanic cases. ERICH-Gene will combine additional ICH cases from around the world to maximize the power of our study to identify novel genetic variants across ethnicities. The new goal is to perform centralized genotyping of 5,200 new ICH cases under the ERICH-Gene Study with case harmonization of advanced clinical and neuroimaging phenotypes. These data will be de-identified prior to sharing in accordance with NIH dbGap broad data sharing regulations. De-identified data may be shared for future studies according to NIH road data sharing requirements.

Given the devastating nature of ICH and the data provided, a randomized double blinded, placebo-controlled pilot trial of fingolimod plus best standard of care management versus placebo plus best standard of care management in the treatment of ICH is justified. First, given the long half-life of fingolimod, this study will assess the safety of single dosing of fingolimod to be given to critically ill patients, considering that a large portion of patients with ICH requires a prolonged ICU stay (the rate of nosocomial infections in the ICH patient population is approximately 23.1%⁸², and the incidence of clinically significant bradycardia after the first dose has been reported in 0.5%⁶⁰). Secondly, we will explore the use of T and B cell subsets as biomarkers of drug effect in this critically ill patient population. And finally, we will be evaluating for any differences in clinical outcomes during an extended 365 day period and perihematomal edema on radiographic imaging.

Objectives:

Specific Aim #1: Assess the safety of a single dose of fingolimod in patients who present with ICH.

Hypothesis #1: We hypothesize that there will be no difference in adverse events compared with placebo, as defined by a) drug-related adverse events; b) nosocomial infections; and c) neurologic decline.

Specific Aim #2: Evaluate the use of CD4+ T, CD8+ T, and CD19+ B cells as biomarkers of drug effect in a critically ill ICH population.

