- All adverse events to be monitored from admission until day of discharge and at all follow up visits. These will include a) clinically significant cardiac events, b) nosocomial infections, and c) neurologic decline.
 - Clinically significant cardiac events: All subjects will be placed on telemetry for 72 hours after administration of drug and changes in heart rate or rhythm will be recorded. Maximal decrease in heart rate occurs within 6 hours of drug administration and recovers, with only 0.5% of patients experiencing clinically symptomatic bradycardia.⁶⁰
 - Nosocomial infections: All UTI, sepsis, and pneumonia events will be recorded and compared to published ICH nosocomial infection rates (23%).⁸²
 - Neurologic decline: Throughout hospitalization, all subjects will be monitored for neurologic decline, which has been reported to occur in up to 33% of patients within the first 48-72 hours.⁸³ Each subject will be assigned a GCS score and NIHSS score at time of enrollment, Day 1, 3, 5, 7, and 14 (discharge dependent). As per ischemia stroke criteria, a change ≥ 4 in the NIHSS will be considered a neurologic change and will be followed over time.
 - Additionally, during hospitalization and at all follow up visits, we will monitor for all drug related and other adverse events, not limited to hepatic function, in-hospital mortality, 30-day mortality, 90-day mortality, and all-cause mortality.

IV. Outpatient follow-up:

Follow-Up Visit 1 (30 ± 14 days after admission)

Standard of care in-person follow up visit to assess neurologic status and functional recovery based on the outcome measures above. At this time, a standard of care Neuroimaging of the brain will be done to follow the resolution of perihematomal edema and to assess for delayed hydrocephalus. 10 cc of blood will also be drawn for standard of care studies (CBC with differential and lymphocyte subset analysis, CMP), in addition to 5 cc set aside in storage for future multi-omic analysis. Any potential long-term drug adverse effects are to be followed at this time.

Follow-Up Visit 2 (90 ± 14 days after admission)

Standard of care in-person follow up visit to assess neurologic status and functional recovery based on the outcome measures above. At this time, there will be a standard of care Neuroimaging of the brain to follow the resolution of both the hematoma and perihematomal edema. Any potential long-term drug adverse effects will be followed at this time.

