- **Aim 1. Safety of a single dose of fingolimod in ICH patients.** The purpose of the primary analyses will be to measure safety and feasibility of the intervention (rates of drug-related adverse events, nosocomial infections, and neurologic decline), and to measure these in the comparison group to help inform feasibility and elements of design for a future trial. In general, we will estimate composite outcome rates (95% CIs) in our study groups, for example of UTI, sepsis, and hospital-acquired pneumonia events, and we will compare these rates to historical rates, when available. This will help ensure the rates of adverse events are not elevated, and are comparable or lower than those in previous reports. Baseline demographic and clinical characteristics will be described and

compared between medical management groups, and differences may be used to help explain heterogeneity in the safety outcomes.

- **Aim 2. Evaluate CD4+ T, CD8+ T, and CD19+ B cells as biomarkers of drug effect in a critically ill ICH population.** To provide initial assessments of ‘clinical activity,’ we will compare inflammation-related biomarkers between the fingolimod and placebo groups over time. In general, we will calculate individual-level changes in the biomarkers from baseline to the later biomarker collections. For example, changes in CD4+ and CD8+ T cells and CD19+ B cells at 24 hr, 72 hr, 5-7 days, and 30 days will be useful to evaluate if levels of inflammation are lower with fingolimod. Prior to analysis, summary statistics and graphic approaches will be used to examine data distributions, both overall, and by study group. Changes will then be compared between the groups using the two-sample *t* test or Wilcoxon rank sum test and alpha level = 0.05 (two-sided). These initial assessments will be interpreted cautiously, given the small sample sizes and possible missing data.

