- **Aim 3. Evaluate differences in mortality and disability between placebo and treatment groups.** Analyses will provide 1) initial percentages of patients who benefit from intervention, specifically focusing on clinical improvements as measured by items from the NINDS Common Data Elements for Stroke, and will provide 2) estimates of variability and correlations in our sample over time. Additional analyses will explore correlations between biomarkers, or their changes over time, including with the perihematomal edema volume. Though the sample sizes in this pilot trial are quite small, these outcome measures have been used extensively in other studies, and our estimates will be helpful to assess comparability in this context, thus informing sample size calculations for a future trial.
- **Aim 4. Perform future multi-omics characterization regarding the immune response related to ICH.** RNAseq Data Analysis: Alignment of reads will be performed using the STAR sequence aligner,⁸⁴ and gene counts determined using feature Counts software.⁸⁵ Differential gene expression (DEG) will be analyzed using DESeq2 software.⁸⁶ All experimental conditions will be prepared in the same experiment, so that the paired-sample analysis can be calculated to detect DEGs at each time point using DESeq2 as described.⁸⁷ Although the primary purpose is to estimate parameters for subsequent power analysis, current analysis will consider Benjamini-Hochberg false discovery rate (FDR) adjusted p<0.05 as significant.⁸⁸ DEGs will be analyzed for significant enrichment of biological pathways and signaling networks using Ingenuity Pathway Analysis (IPA), Causal Network Analysis and Upstream Regulator Tools⁸⁹ and the DAVID software as described.⁹⁰ A parallel analysis to the detection of DEG will be computed on the percent methylation (i.e., estimation of parameters for future power calculations and study design, FDR-adjusted p-values). Further statistical analyses will necessarily rely on data descriptions, and the formal statistical inference (hypothesis testing) will be limited due to the small sample size (n=10).

Human Subjects Protection:

The investigator will ensure that this study is conducted in full conformity with Regulations for the Protection of Human Subjects of Research codified in 45 Code of Federal Regulations [CFR] Part 46, 21 CFR Part 50, 21 CFR Part 56, 21 CFR 312, and/or the International Council on Harmonisation E6.

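### Aim 1 specifies no randomised fingolimod-minus-placebo safety difference, although Hypothesis 1 is against placebo, and its assurance that adverse event rates are not elevated goes beyond what the design supports

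*Combined protocol and SAP*

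**What the plan says.** Under Objectives, Hypothesis 1 for Specific Aim 1 reads: "We hypothesize that there will be no difference in adverse events compared with placebo". The events in question are drug-related events, nosocomial infections and neurologic decline.

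Statistical Analysis, Aim 1, says that these rates will be measured under the intervention and in the comparison group, and that rates with 95% confidence intervals will be estimated in the study groups. For the outcomes it then adds: "we will compare these rates to historical rates, when available", and draws the inference "This will help ensure the rates of adverse events are not elevated, and are comparable or lower than those in previous reports". The one between-group comparison in Aim 1 is of baseline characteristics, of which it says "differences may be used to help explain heterogeneity in the safety outcomes". No interval method, margin or threshold for an elevated rate is given.

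The section on adverse events follows the same line for infection, setting the trial's events against a published 23% (23.1% in the rationale).

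The other aims differ. Aim 2 states: "we will compare inflammation-related biomarkers between the fingolimod and placebo groups over time", and names tests and an alpha level. Aim 3 is headed "Evaluate differences in mortality and disability between placebo and treatment groups", but its body plans percentages who benefit, variability and correlations, with no between-arm estimator.

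**The concern.** The trial is randomised, double-blind and placebo-controlled, and safety is its primary outcome. The hypothesis needs a contrast between the randomised arms, but the analysis section directs the safety comparison to published rates. Those come from other patients, definitions and periods. A rate above or below them could reflect patient selection or the observation window rather than the drug.

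The study is meant to inform a future trial. If Aim 1 is reported as written, a handful of events near the published rate could be presented as reassurance, and that conclusion could be carried into the next design. The placebo data that would put the rate in context will have been collected, but the difference and its interval would be unplanned.

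**Working it through.** **Step 1: does Aim 1 contain the contrast?** It has rates with intervals by group, placebo included. It has a comparison of those rates with historical ones, and a comparison of baseline characteristics between groups. It has no difference, ratio, interval for a difference or test between fingolimod and placebo for a safety outcome.

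**Step 2: do the historical figures match the primary outcomes?** These are the plan's own figures, from the adverse events section and Outcome Measures.

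| Component | Historical figure | Primary outcome |
|---|---|---|
| Neurologic decline | up to 33%, within 48-72 hours | at 30 days |
| Cardiac | 0.5%, symptomatic bradycardia only | all clinically significant cardiac events at 30 days |
| Nosocomial infection | 23%, no window stated | at 90 days |

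The first two differ in window or event type. The third cannot be checked. Concurrent placebo patients share the trial's windows, definitions and selection.

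**Step 3: arm size.** Sample Size gives 30 in total and 10 open-label, with no formula to reproduce. Allocation is equal. If the 10 are part of the 30, each randomised arm has (30 − 10)/2 = 10. If they are additional, each has 30/2 = 15. Neither is stated, so both are shown.

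**Step 4: what a single-arm interval can tell apart (infection).** The benchmark is 23.1%; doubled it is 46.2%, halved 11.55%. Because no method is named, three are used:
- exact: the 2.5% quantile of Beta(x, n−x+1) to the 97.5% quantile of Beta(x+1, n−x)
- Wilson: [p + z²/2n ± z√(p(1−p)/n + z²/4n²)] / (1 + z²/n), with z = 1.96
- Jeffreys: quantiles of Beta(x+½, n−x+½)

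| Count | Exact | Wilson | Jeffreys |
|---|---|---|---|
| 2/10 | 2.5-55.6% | 5.7-51.0% | 4.4-50.3% |
| 3/15 | 4.3-48.1% | 7.0-45.2% | 6.0-44.4% |
| 0/10, upper limit | 30.8% | 27.8% | 21.7% |
| 0/15, upper limit | 21.8% | 20.4% | 15.2% |

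*Not elevated.* At n = 10 the upper limit falls below 46.2% only for 0 or 1 event, by all three methods. If the true rate is 23.1%, the chance of failing to exclude a doubling is P(X ≥ 2) = 1 − 0.769¹⁰ − 10 × 0.231 × 0.769⁹ = 1 − 0.0723 − 0.2172 = 71%. At n = 15 exclusion needs at most 2 events (exact) or at most 3 (Wilson, Jeffreys), so the chance of failing is P(X ≥ 3) = 71% or P(X ≥ 4) = 47%.

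*Lower.* At n = 10, 0/10 excludes 23.1% only by Jeffreys. If the true rate were halved, 0/10 occurs with probability 0.8845¹⁰ = 29%. At n = 15 only 0/15 shows a lower rate, with probability 0.8845¹⁵ = 16%.

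*Elevated.* A true doubling puts the interval wholly above 23.1% with probability 28.8% (exact or Jeffreys, at least 6/10) or 52.7% (Wilson, at least 5/10). At n = 15 it is 38.2% (exact) or 58.5% (Wilson, Jeffreys). Wilson's advantage at n = 10 comes with more false flags at 23.1% (5.8% against 1.3%).

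**Step 5: what the missing contrast would deliver.** The Newcombe limits for a difference d = p₁ − p₂, with Wilson limits l and u for each arm, are d − √[(p₁−l₁)² + (u₂−p₂)²] and d + √[(u₁−p₁)² + (p₂−l₂)²]. For 2/10 v 2/10 the half-width is √[(0.200−0.057)² + (0.510−0.200)²] = 0.341, so the interval is −34 to +34 points. For 3/15 v 3/15 it is −28 to +28 points. With true rates of 46.2% v 23.1% the interval excludes zero 16% of the time (10 per arm) or 27% (15 per arm).

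**The case against.** The strongest reply is that this is a declared pilot with an estimation purpose. Rates with intervals in each arm are a defensible choice, and the assurance sentence is hedged by its opening verb and by the qualifier on historical rates. The contrast would be so imprecise that it could neither support nor refute Hypothesis 1. All of that is fair, and low power is not the fault alleged. What remains is that the plan leaves out the estimate its hypothesis refers to and attaches a conclusion to a comparison that cannot carry it.

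Three stronger readings are tempting, and the documents do not support them.

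- *That the placebo arm is ignored for safety.* Aim 1 says rates are measured in the comparison group and reported with intervals. A reader could subtract one rate from the other. Only the planned difference and its interval are absent.
- *That the gap is peculiar to Aim 1.* Aim 3 contrasts the arms only in its heading; its body names no between-arm estimator. Only Aim 2 specifies one.
- *That the study cannot rule out a doubling of infection risk.* This depends on arm size, count and method. At 3/15 the Wilson and Jeffreys upper limits (45.2% and 44.4%) fall below 46.2%. Pooling all fingolimod patients on the 10 + 10 + 10 reading gives n = 20, where 4/20 excludes a doubling by all three methods (5/20 does not) and the chance of failing drops to 51%. Aim 1 plans no such pooling, and the open-label patients are non-randomised and dosed by tube, so this case is a bound, not the planned analysis.

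**Conclusion.** The point holds as a specification gap with an over-strong claim attached, and should be fixed. Aim 1 does not specify the randomised difference that Hypothesis 1 implies. Its only named outcome comparator is a set of historical figures that differ from the primary outcomes in event type or window, or have no stated window. At the infection count nearest 23.1% under the 10-per-arm reading, the interval holds both the benchmark and twice the benchmark. The chance of failing to exclude a doubling when nothing is wrong is 71% at 10 per arm, and 47% to 71% at 15.

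This rests on an inferred arm size, on doubling as our yardstick, and on interval exclusion as a device to show precision; the plan sets no decision rule. The textual finding depends on none of these. The expectation of no difference in Hypothesis 1 is as hard to support at this size as the assurance in Aim 1.

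**What to change.** 1. For each primary safety component (cardiac events, nosocomial infection, neurologic decline), report the fingolimod-minus-placebo risk difference in randomised patients with a 95% interval, for example Newcombe, as a descriptive estimate without a test. Report the non-randomised open-label arm separately.
2. Keep historical rates as context only, and state any mismatch in event type or window beside each.
3. Confirm the randomised arm size, name the interval method, and replace the assurance sentence with the precision at that size. For example: *If 10 per arm, 0/10 events has an exact upper 95% limit of 31% and 2/10 an exact interval of 3-56%; the study is not sized to show that rates are not elevated.* Soften the no-difference wording of Hypothesis 1 in the same way.

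The cost is SAP wording and a few table rows, with no new patients, visits or data. The downside is that the contrast is wider than the single-arm intervals and the stated safety claim becomes less favourable. The gain is a concurrent randomised comparator and a claim that the data can carry.

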 - Obtained at time of admission for standard of care baseline set of admission labs, to include CBC with differential with a baseline lymphocyte subset analysis, basic metabolic panel, liver function panel (LFTs) to rule out underlying hepatic dysfunction, and coagulation panel to rule out underlying coagulopathy.
 - If they meet all eligibility criteria, prior to the administration of study drug, 5 cc of blood will be set aside in storage for future multi-omic analysis.

- Pregnancy test:
 - For women of child-bearing age, obtained at time of admission as part of standard of care.
- Urinalysis:
 - As part of admission standard of care to rule out UTI as cause of alterations in mental status.
- Neuro imaging: Most appropriate clinically indicated standard of care
 - CT scan of the head to evaluate for ischemic infarct or intracerebral hemorrhage
 - CT angiogram of the head and neck to be obtained as part of standard of care work up to exclude vascular etiologies of hemorrhage. If a CTA is contraindicated due to renal impairment, an MRA will be performed instead.
 - MRI of the brain to be obtained as part of standard of care work up to exclude neoplasms or cavernous malformations as etiology of hemorrhage.
- Speech and swallow evaluation to assess for any dysphagia, important for exclusion criteria. This procedure occurs as part of standard of care. A bedside swallow evaluation is appropriate.

II. For participants who meet the inclusion criteria, without exclusion criteria, and are enrolled in the study:

- Each participant is to be admitted to the Neuroscience Intensive Care Unit for standard of care close neurologic monitoring, vital signs as part of standard of care, intracranial pressure and drain output monitoring if an EVD is in place.
- Those participants randomized to the fingolimod plus best standard of care group will receive a single dose of 0.5 mg oral fingolimod within 24 hours of symptom onset. Those participants randomized to the control group will receive a single dose placebo pill within 24 hours of symptom onset that will appear, smell, and taste identical to the fingolimod capsule.
- For participants who are eligible for the open-label arm, they will receive a single dose of 0.5 mg fingolimod through an NGT or Dobhoff tube within 24 hours of symptom onset.

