Follow-Up Visit 3 (180 ± 14 days after admission)

In-person follow up visit to assess neurologic status and functional recovery based on the outcome measures above. Any potential long-term drug adverse effects will be followed at this time. At this time, there will be a Neuroimaging of the brain to follow the resolution of both the hematoma and perihematomal edema. Any potential long-term drug adverse effects will be followed at this time

Follow-Up Visit 4 (365 ± 14 days after admission)

In-person follow up visit to assess neurologic status and functional recovery based on the outcome measures above. Standard of care Neuroimaging will be performed to assess brain injury and atrophy.

	Enrollment	24 hrs post -	72 hrs post - ictus	5-7 days	10-14 days	Discharge	30±1 4 days	90±14 days	180±14 days	365±1 4 days
--	------------	---------------	---------------------	----------	------------	-----------	-------------	------------	-------------	--------------

		ictus +									
Neuroimaging Diagnostic CT,CTA,MRA or MRI	X	X	X	X	X [‡]			X	X	X	X
Medical history	X										
ICH score	X										
EKG	X										
Speech and swallow evaluation	X										
Informed consent	X										
Single drug dose (fingolimod or placebo)	X										
CSF*	X*	X*	X*	X*	X*						
Peripheral whole blood (CBC, CMP, lymphocyte subsets)	X	X	X	X	X [‡]			X			
Telemetry	X	X	X								
Vital signs	X	X	X	X	X			X	X	X	X
Neuro exam	X	X	X	X	X			X	X	X	X
NIHSS	X	X	X	X [†]	X [†]	X	X	X	X	X	X
mRS	Historic			X [†]	X [†]	X	X	X	X	X	X
PROMIS 10				X [†]	X [†]	X	X	X	X	X	X
MoCA				X [†]	X [†]	X	X	X	X	X	X
WAB-R				X [†]	X [†]	X	X	X	X	X	X

* If the participant requires EVD placement.

†Or at time of discharge

‡ If still hospitalized or clinically indicated

+ At least 6 hours after medication given

Outcome Measures:

Primary outcome measure:

- Safety of a single-dose administration of fingolimod to critically ill patients. We will be assessing rates of the following adverse events:
 - Clinically significant cardiac events at 30 days
 - Nosocomial infections (UTI, sepsis, and pneumonia) at 90 days
 - Neurologic decline, considered a change ≥ 4 points of the NIHSS at 30 days

Secondary outcome measures:

- Feasibility of administering fingolimod through an NGT or Dobhoff tube.
- Changes seen in the lymphocyte subpopulations at 30 days. The lymphocyte subsets of CD4+ T, CD8+ T, and CD19+ B cells will be compared among the three groups and the trends will be followed over time in all participants.

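### Aim 2 tests raw changes from baseline without adjusting for the baseline count, and the plan does not say whether the open-label arm enters the comparison

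*Combined protocol and SAP*

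**What the plan says.** Statistical Analysis, Aim 2, states that "we will compare inflammation-related biomarkers between the fingolimod and placebo groups over time". The method is: "we will calculate individual-level changes in the biomarkers from baseline to the later biomarker collections". Changes at 24 hours, 72 hours, 5-7 days and 30 days are then compared by two-sample t test or Wilcoxon rank sum test at a two-sided 5% level. Beforehand, "summary statistics and graphic approaches will be used to examine data distributions", overall and by group. No covariate or model is named. The section adds: "These initial assessments will be interpreted cautiously, given the small sample sizes and possible missing data".

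The baseline value exists. Under Interventions and Interactions, the admission blood work is "to include CBC with differential with a baseline lymphocyte subset analysis", and the schedule of assessments marks lymphocyte subsets at enrolment.

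On the groups, the secondary outcome measures say that "CD4+ T, CD8+ T, and CD19+ B cells will be compared among the three groups". The third group receives open-label fingolimod by feeding tube, and the Randomization section says that entry to it is not randomised.

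**The concern.** There are two separate issues.

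1. **Precision.** Subtracting the baseline fixes its slope at 1, whatever the data show. ANCOVA estimates the slope, and in a trial this small the difference can be material. The change score also carries chance baseline imbalance into the estimate: if fingolimod patients happen to start higher, regression to the mean looks like a fall caused by the drug.
2. **Who is compared.** A two-sample test cannot carry out a three-group comparison. The plan does not say whether open-label patients are left out, pooled with randomised fingolimod or compared separately. A contrast that includes them loses the protection of randomisation.

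**Working it through.** **Inputs.** The Sample Size section gives 30 subjects in total and 10 in the open-label arm; allocation is equal. If the 10 are within the 30, there are (30 − 10)/2 = 10 per randomised arm; if they are additional, there are 15. The documents give no subset SD, correlation or effect size, so there is no planned figure to reproduce. Assumed quantities: r, the correlation of baseline with follow-up, and k, the baseline SD divided by the follow-up SD.

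**Variance.** With the follow-up SD set to 1 and n per arm:

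- change score: 1 + k² − 2rk = (1 − r²) + (k − r)²
- ANCOVA: (1 − r²)f, where f = 1 + 1/(2n − 4) is the small-sample cost of estimating the slope; f = 1.0625 for n = 10 and 1.0385 for n = 15.

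Example with n = 10, k = 1, r = 0.3: 1.4/(0.91 × 1.0625) = 1.448.

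Variance of change score divided by variance of ANCOVA:

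| n per arm | k | r = 0.3 | r = 0.5 | r = 0.7 |
|---|---|---|---|---|
| 10 | 0.8 | 1.200 | 1.054 | 0.960 |
| 10 | 1.0 | 1.448 | 1.255 | 1.107 |
| 10 | 1.2 | 1.779 | 1.556 | 1.403 |
| 15 | 0.8 | 1.228 | 1.079 | 0.982 |
| 15 | 1.0 | 1.481 | 1.284 | 1.133 |
| 15 | 1.2 | 1.820 | 1.592 | 1.435 |

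**Worst case for ANCOVA.** The ratio is smallest at r = k, where it equals 1/f: 0.941 (n = 10) or 0.963 (n = 15). ANCOVA's variance is therefore never more than about 6% or 4% larger.

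**Break-even.** For k = 1 the two are equal at r = 2/f − 1, which is 0.882 (n = 10) or 0.926 (n = 15). For k = 0.8 the gain is first lost at r = 0.600 or 0.651 and returns above 0.906 or 0.890. For k = 1.2 there is no break-even.

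**Interval width.** Simulated median 95% CI half-width, ANCOVA relative to change score, n = 10, at r = 0.3, 0.5, 0.7 (40,000 normal replicates): 0.91, 0.97, 1.02 for k = 0.8; 0.83, 0.89, 0.95 for k = 1; 0.75, 0.80, 0.85 for k = 1.2.

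**Rank-based version.** Simulated power of the Wilcoxon test on changes against the Wilcoxon test on residuals of follow-up regressed on baseline with the arms pooled. Here n = 10, with 20,000 normal replicates, and the effect is set where ANCOVA has about 80% power:

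| k | r = 0.3 | r = 0.5 | r = 0.7 |
|---|---|---|---|
| 0.8 | 67% v 75% | 73% v 74% | 77% v 74% |
| 1.0 | 59% v 75% | 65% v 74% | 71% v 74% |
| 1.2 | 50% v 74% | 56% v 74% | 61% v 74% |

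Simulated type I error was 0.040 to 0.054 across all four tests (t, ANCOVA and the two Wilcoxon tests).

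**Chance imbalance** (k = 1, n = 10). The SE of the baseline mean difference is √(2/10) = 0.45 SD. In simulated trials where fingolimod starts higher by more than 1 SE, the change-score estimate is shifted by about −0.48, −0.34 and −0.21 SD at r = 0.3, 0.5 and 0.7. The ANCOVA shift is about 0.

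**The case against.** The strongest reply is that the planned test is valid, that Aim 2 is secondary in a pilot, that no decision depends on its p-values, and that change is what the hypothesis is about. All of this stands, and it keeps the severity low. It does not recover lost precision: ANCOVA estimates the same treatment effect from the same pairs of values.

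Second, r and k are assumed, and the grid runs from a 4% loss to an 82% gain in variance terms. That also stands. The case for adjusting rests on the bounded downside, not on any one cell.

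Third, some of the benefit may come from the log scale and not from the covariate. As an illustration, borrow the fall in total lymphocytes to about 60% of baseline from section 1.4, with 10 per arm, log SDs of 0.5 and r = 0.7. Moving the change score from raw to log scale raises power from 57% to 79%, and the covariate takes it to 83%. With log SDs of 0.5 at baseline and 0.4 at follow-up and r = 0.5, the covariate alone raises it from 65% to 85%. With 0.4 and 0.5 and r = 0.7 it costs a little, 85% to 83%. Scale and covariate are separate choices, and both need stating.

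Fourth, choosing scale or test after seeing the data by group is loose. The plan already has this weakness; the fix should not carry it forward.

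Fifth, the two statements on groups may be compatible: a three-group description plus a two-group test. That is possible, but neither section says so.

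**Conclusion.** The concern holds on both counts and is modest in size. The unadjusted change-score test is valid but usually less precise than ANCOVA. With 10 per arm and equal SDs, its variance is 45%, 25% or 11% larger at r = 0.3, 0.5 or 0.7; the excess is gone at r of about 0.88. If follow-up counts vary more than baseline counts (k = 0.8), the gain is smaller and can reverse slightly. These figures rest on assumed r and k, normal data and 10 or 15 patients per randomised arm. No absolute power for this trial is claimed. The mismatch over groups is plain from the text, carries no figure, and needs one clarifying sentence.

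**What to change.** - **Main analysis.** For each subset and visit, in the randomised arms only, analyse the follow-up count by ANCOVA on arm and baseline count. Use the log scale if the planned distribution check supports it, and then report the fingolimod/placebo ratio with its 95% CI; otherwise report the adjusted difference with its 95% CI. A ratio matches section 1.4, which expresses the drug effect as a percentage of baseline. Choose scale and test without sight of the arms.
- **Rank-based alternative.** Replace the plain Wilcoxon test by a Wilcoxon test on the residuals of follow-up regressed on baseline with the arms pooled. With no drug effect these residuals do not depend on arm labels, so the level is kept. Report the ANCOVA estimate and interval beside it. ANCOVA on ranks is not advised: at r = 0.9, k = 1 and 10 per arm it had 66% power against 76% for the Wilcoxon test on changes.
- **Groups.** State in both sections that the formal comparison is randomised fingolimod against placebo, with no open-label patients pooled in. Report the open-label arm's changes descriptively with 95% CIs. These may also inform tube delivery; that is an inference, since the protocol does not say so.

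**Cost.** Wording only, with no new data. The variance loss is at most about 6% (10 per arm) or 4% (15). One degree of freedom is lost, which makes the t critical value 0.4% or 0.2% larger. The adjusted rank test loses at most about 3 points of power in the grid (77% to 74%). On the log scale the result is a ratio instead of a difference in counts, and zero counts need a stated rule.
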